- Patients: The benefits of audio recording with analysis of specified outcomes, which are essential to the study, is that it will enable an assessment of whether this technology enhances patient health care outcomes as well as understanding of their care. Anticipated risks for patients included that: (a) carrying an audio recorder into a visits could be an inconvenience, could make them feel uncomfortable about disclosing private information. We minimize these risks by assuring you that if you are always welcome to turn of the audio recorder during the visit if you decide you don't want to participate for any reason. We also minimize these risks by informing you that your audio recording is managed and stored with a comparable level of data protection and security as your medical record; (b) There is the possibility that there could be a breach in confidentiality due to a data security failure related to the storage or transmission of an audio file, including during collaboration with the Dartmouth team. The reason we are working with this group is that they have developed the technology, which is currently not available within the VA. They have minimized the risk to loss of confidentiality by using the best available software systems and data security protocols which are the same or comparable to VA systems. While we cannot say how likely a data breach is, we estimate the risk to be small; (c) Some of the audio recordings will be listened to by one or more research assistants. This will occur to a random sample of 10% of audio recorded visits. The research team will minimize risk of breach of confidentiality by directly uploading the audio file to the secure HealthPAL server. (d) A VA data analyst will look up patient specific information in the CDW about blood pressure, blood sugar, emergency department and hospitalization usage, prescription refill rates and appointment attendance, but will not have access to the medical record. The privacy will be minimized by keeping patient names separate using a crosswalk file. (e) The audio recording process could possibly undermine a patients relationship with their doctor. We have minimized this possibility by only including physicians and other health care providers who want to participate and have consented to participate; (f) As explained above there are three brief questionnaires patients will or may be asked to complete. The first is the brief assessment of their knowledge and comfort with medical terminology. All participating patients do that one. The second is a brief survey just as they exit their visit and return the audio recorder. That questionnaire will ask them about whether they found the experience valuable, how much effort it took, and whether they were comfortable participating. There is about a 25% chance they will be asked to do this questionnaire. The third questionnaire is conducted by phone 1-2 weeks from their

visit and is intended to find out how confident and comfortable they are managing their health needs and care plan. There is a 45% chance they will be called to complete this questionnaire. On all three questionnaires the research team will substitute a study identification code in place of their name, so that if anyone were to find the data they would not know that it is about a particular patient. We'll keep the study ID code sheet that contains the names of all study participants with their study IDs, in a separate secure location on a server that also belongs to the VA (i.e. a crosswalk file). That sheet will be deleted at the end of the study. There may be some risk in sharing slightly personal data, including how knowledgeable you are about medical terms, and how comfortable you are managing their own care. They may find sharing this information personally uncomfortable. We minimize this risk by assuring you that if, for any reason, you wish not to answer specific questions you need not do so.

- Providers: The benefits of audio recording with analysis of provider experience, is that it will enable an assessment of whether this technology enhances patient health care outcomes as well as understanding of the providers perspective, which is essential to long term implementation planning. Risk and mitigation of risk include that providers: (a) may feel some unease that their interaction with their patient is being recorded and that they may listen to it and share it with others, such as caregivers and family. Any audio shared with patients will be streamed so patients will not have access to an audio file that can be uploaded to a third-party site; (b) There is the possibility that there could be a breach in confidentiality due to a data security failure related to the storage or transmission of an audio file. We will be using a crosswalk file as detailed directly above, with assignment of a discrete code for physician and patient, assigned to each audio and related instruments used for audio coding, such as the SEGUE. Audio data in arm 1 – the arm that shares audio with the patient and provider -- will be uploaded directly to the HealthPAL website(<https://va.audiohealthpal.com>) managed by *Geisel School of Medicine at Dartmouth* where a research team specializes in managing patient audio recorded data. The VA cannot vouch for the security of the system nor take responsibility for any breaches. The reason we are working with this group is that they have developed the technology, which is currently not available within the VA. They have minimized the risk to loss of confidentiality by using the best available software systems and data security protocols which are the same or comparable to VA systems. While we cannot say how likely a data breach is, we estimate the risk to be small; (c) Providers will be invited to participate in two brief survey's over the course of the three year study. Additionally, the providers will be invited to participate in two focus groups where their names will be replaced by a code and linked to a crosswalk file. Because the information we are obtaining is not sensitive – it is solely about the experience of the providers participating in this study, , risks of participation are small but there could be some inconvenience. They are welcome to abort them at any time.

Leadership interviews: The benefits of leadership interviews is that the data collected on their perspective will inform efforts to disseminate and implement patient collected audio more broadly if the findings demonstrate it is effective. These interviews, which will be recorded, will be voluntary, coded and linked to a cross walk document. The recording will be heard by members of the research team. There is a minimal risk of breach of confidentiality, and the data collected is not sensitive as it does not include discussions of any specific patient's care or of any particular provider.

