We have designed a three arm RCT (figure 2, below), with each arm varying as to who gets access to the audio after the visit and who is aware of the fact that audio recording is occurring during the visit. The design establishes the conditions for achieving the first two aims of the study, with each aim framed as testable hypotheses. Arm 1 is the intervention, with both provider and patient aware of the recording. It is designed to represent how OAA would be utilized in actual practice. In Arm 2 all parties are also aware of the audio recording, but this time neither gets access to the audio after the visit (although the research team does). Arm 2 is a control for isolating the effect of patient access after the visit to the audio in Arm 1. Both patient and physician are blind to whether they are in Arm 1 or 2 until after the visit. Comparing these two arms will achieve the first aim of the study. Arm 3 is a second kind of control, as the audio is again not shared with the patient. In this arm, however, the patient conceals the audio recorder, typically in an accessory such as an eye glass case (a method we have employed extensively¹⁴), so that the provider is unaware they are being audio recorded until after the visit, enabling the research team to achieve the second aim of the study by comparing Arm 3 to Arm 2, isolating the effect of being aware they are being audio recorded on the provider's interactions with the patient. Whereas in Arm 3 the physician is unaware they are being recorded, in Arms 1+2, they are aware and also know there is a 50% chance the patient will have access to the audio. This design enables Arm 2 to serve both as a control for Arm 1 to achieve Aim 1 (since patient only gains access to the audio in Arm 1) and as comparator with Arm 3 – to achieve Aim 2 -- since the physician believes the patient may gain access to the audio.

[figure not shown]
Figure 2: Study Design

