The superscripts associated with each outcome in the “How Answered” boxes in figure 2 refer to the following strategies for testing the hypotheses in Aims 1 and 2: (a) A survey called the Patient Activation Measure (PAM), (Appendix A-1) is completed by patient 1-2 weeks after their visit²²; (b) The “no show rate” is the inverse of Return Visit Adherence (RVA) rate;²³ (c) the Refill rate is “proportion of days covered” (PDC), a metric CMS utilizes in its plan ratings;²⁴ and (d) BP and HgB A1c are checked if they are repeated within 6 months; (e) The SEGUE Framework for evaluating and scoring communication behavior, as rated off of the audio recording by a research assistant utilizing a checklist (Appendix A-2)²⁵ and (f) Content Coding for Contextualization of Care, also called “4C”²⁶. Note: (b-d) are extracted from the CDW and SEGUE and 4C completed while accessing the medical record and listening to the audios. Finally, for all three arms, the members of the research team collecting the data and coding the audio are blinded as to study arm. There is no arm in which the patient is unaware a visit is audio recorded. Blinding the patient is not pertinent to achieving the aims of the study.

Figure 3, the flow diagram below, allocates patients in a parallel three arm randomized controlled trial (RCT) to most efficiently achieve the aims of the study (the calculations for the specific sample sizes are justified later in the protocol – and shown in Tables 4.1 and 4.2. on pp 24+25).

Figure 3: Flow diagram for parallel RCT

Random assignment to arms will be made using computer-generated sequences within the diabetes clinics (1:1 randomization to Arms 1 and 2 in blocks of 4) and primary care clinics (5:5:2 randomization to Arms 1, 2, and 3, in blocks of 24, with one partial block of 8 patients). Solid lines represent unconditional allocation of participants to Arms; dashed lines represent random sampling of participants to create efficient unbiased subsamples for key hypothesis tests. The rationale for the design, starting at the top of the figure and working down, is as follows:

- We start with two separate pools, diabetes and primary care clinics, because measurement of the effect of OAA vs control (Arm 1 vs Arm 2) on Hgb A1c is most efficiently accomplished

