For assessing provider behavior change based on awareness that the patient may get the audio recording and listen to it to better understand their care, we are focusing on both the process and content of the interaction. We selected SEGUE both because of its high evidence for concurrent and construct validity, and inter-rater reliability, and because it can be scored by an independent third party off of audio using a checklist.²⁷ Whereas SEGUE is a process measure (how effectively a provider communicates without regard to the content of the discussion), 4C is a content measure, i.e. whether they follow up on what the patient needs regardless of how they go about it. 4C is coded by a trained RA with access to the medical record and audio recording; the RA documents clues that a patient is struggling with life issues complicating their care ("contextual red flags"), whether the provider asks about them ("contextual probes"), whether the patient reveals the underlying life challenges ("contextual factors") and, if so, whether the physician addresses them ("contextualized care").²⁸ Contextual red flags are specific pre-determined variable extracted both from the medical record (including specific thresholds for missed appointments, emergency department visits, and medications that have not been refilled). 4C has strong published evidence for both construct validity and inter-rater reliability (90%),²⁶ and contextualized care significantly predicts a range of favorable patient health care outcomes.¹⁴ Notably, we have observed that physicians are more likely to contextualize care when they know they are being recorded.¹³ We have previously documented that communication performance and contextualization of care are separate constructs that do not correlate -- so must both be measured to fully assess patient centered provider behaviors.²⁹ Note that at the time of the coding, including completion of the SEGUE instrument, the audio coder will only have access to the designated codes for provider and patient, which will be utilized for tracking purposes. This is because the first step when audio recordings are uploaded following each encounter is to assign them codes with provider and patient names stored separately to a cross walk file.

Audio recording technology

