For the audio recording device, we plan to use VHA approved audio recorders with accompanying software, the DS-9000 and DS 9600 Olympus encrypting recorders with a pin code for security. The audios will be uploaded by the RA to a workstation desktop on to our secure VHA research server, hosted in our Center of Innovation (COIN), using the VHA approved Olympus/ODMS Dictation Module 7. Each audio file name will include the Veterans last name and date of the visit., for Arm 1), The project manager will then trim the audio to remove all the identifiers using the audacity software and upload the deidentified audio directly to the HealthPAL website(<https://va.audiohealthpal.com>) managed by the research team at the

Department of Biomedical Data Science at the Geisel School of Medicine at Dartmouth. At that point an automated script sends an email to the patient and provider (in Arm 1) providing them a link to login to access the audio from any internet enabled device. The Dartmouth system, HealthPAL,²¹ which is specifically designed for sharing audios with patients, also enables patients to selectively share their audio with others, such as family or caregivers, using a highly secure process that enables them to send an invite email and text message with a six digit code, that enables the user to set up their own unique password. This feature additionally enables the research team to track how patients are using audios including whether they are listening to them, how often, whether they share them and whether those individuals access the audios as well. Because many of the patients at participating sites are older and have low levels of technology literacy, we will make an attempt to reach by phone any subject who has not accessed HealthPAL within 7 days following their visit. These data will be variables in our analysis for the outcomes in Aim 1, e.g. for patient activation, medication adherence etc...

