Open Audio team (Dartmouth) to customize and pilot test with assistance of teams in Cleveland and Chicago (WH,PB,SW,CF-Y)			

Open Audio Data Collection (GS, BK, Cleveland RA)											
Outcomes and demographics extracted from CDW for A1c, BP, Adherence measures (BB)											
Survey providers/staff (GS, BK, Cleveland RA)											
exit patient surveys (GS, BK, Cleveland RA)											
PAM survey phone calls post visit (GS, BK, Cleveland RA)											
Focus groups staff (SB)											
SEGUE + 4C Coding of sample of recorded visits (ABC, GS, BK)											
Site leadership interviews (SB)											
Data analysis of outcomes, contextual error rates for each arm of study (AS)											
Dissemination (SW, CF-Y)											

How anticipated risk will be minimized and an analysis of risk vs. potential benefit

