(C) Upon arrival, they will complete the informed consent process and the brief literacy screen (REALM-SF), receive the audio recording device, and instructions based on the arm of the study to which they are randomized, as to whether to keep the audio recording out in the open (Arms 1 and 2), or to conceal it (Arm 3). A code, assigned to the encounter, will be utilized as the ID on the literacy screen, and linked to the patient name and medical record number stored in the cross walk file on a separate VHA approved server. After the encounter, patient and provider participants will receive a link to access the audio if they were in Arm 1. If they are called prior to completing the process, their appointment takes precedence and they will not participate.

(D) In addition to pre-visit outreach, the RA will recruit patients at an information desk on site when they arrive in the waiting area with a poster and a brochure inviting Veterans to learn more if they are interested.* This will occur until recruitment targets are met. Those who are seeing a participating provider and want to participate will complete the informed consent process and the brief literacy screen (REALM-SF). They will receive a \$20 gift card to remunerate them for the additional work of completing the survey after the visit and for randomly participating in a follow up call for the PAM survey. If the Veteran is called prior to completing the process, their appointment takes precedence and they will not participate.

***COVID-19 MODIFICATION: As long as infection transmission remains a risk the following protocol modification will be in place:**

- Only phone based recruitment will occur.
- The informed consent process will be completed over the phone prior to the visit, except for the final signing process.
- The RA will still meet the patient in the waiting area, both masked. However, it will be a very brief meeting and they will remain 6 feet apart. There will be a small fold

up table in the waiting area. The patient will sign the consent form, collecting the audio recorder, and complete the 7 item REALM-SF which consists of reading out loud 7 words, and takes less than 1 minute.

- Post visit, the patient will return the audio recorder to the table and collect \$20 gift card from the research assistant. Again, the RA will maintain a physical distance of at least 6 feet and will remain masked.

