5.3 Informed Consent Procedures

- Indicate if informed consent will be obtained and/or if you are requesting a waiver of informed consent or waiver of documentation of informed consent. If the research involves multiple phases, specify for which phases of the research the waiver(s) is being requested and/or the informed consent will be sought.
- Describe who will be obtaining informed consent, if applicable, and any circumstances that may need to be addressed (e.g. subjects with impaired decision making ability and the use of a legally authorized representative, etc.)
- If applicable, indicate how local site study personnel will be trained regarding human subjects protections requirements and how to obtain and document informed consent.

Providers: As described in recruitment section above, participating physicians and nurse practitioners will complete an informed consent process. As noted, those who wish to participate will sign a sheet providing their name and contact information. The site investigator and/or RA will meet with them to complete the informed consent process.

Patients: As described in recruitment section above, prior to participation but upon arrival for their appointment, patients will complete the informed consent process. As noted, the RA will meet patients (who have already assented by phone) prior to their appointment to complete the consent process.

All personnel will complete all mandatory VA training for human subject research and have current certificates.

Hospital Leaders: As explained above, we plan to interview hospital leaders about the program. They are also subjects, but given the low risk to them, we have requested for a waiver of documentation of consent. We will be contacting them via email asking them to participate in the research study by attaching the Informed consent explaining the research study and their participation..

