7.0 Privacy and Confidentiality

- Describe whether the study will use or disclose subjects' Protected Health Information (PHI).

Patient PHI: The study will be collecting PHI, consisting of audio recordings of encounters and patient email addresses, to send them links to their audio files. As noted above, the data analyst will extract the patient outcomes and demographic data from the Central Data Warehouse. He will have access to PHI briefly as he runs search in the Corporate Data Warehouse.

For data tracking purposes, we will create a master spreadsheet with a row for each patient encounter. A code will be assigned to each encounter linked to a cross-walk file (see below).

The three patient surveys (literacy survey, exit survey, and patient activation measure) will be handled similarly: they will be assigned an encounter specific code, with a link to the cross-walk file.

Provider Subject PHI: Survey and focus group data is not PHI. However it is possible that during an employee focus group discussion about the OAA project, that a clinician could mention a patient's name or other identifier. This is not likely as the topic of the focus groups is the OAA project not the care of any specific individual.

- Describe the steps that will be taken to secure the data (e.g., training, authorization of access, password protection, encryption, physical controls, Certificates of Confidentiality, and separation of identifiers and data)

The data encryption and storage methods are highly secure, but are monitored for safety using standard software storage review processes, including log analysis.

All study team members will be required to maintain necessary research training, and the PI of the study team will oversee completion and maintenance of any required training.

The cross-walk file will be kept in a separate file from the master file, accessible only with permission from the PI with access enabled by the IT data manager. Access is based exclusively on need, as follows: The data analyst who access the CDW to look up A1c and BP, RVA and PDC; The RA who completes the PAM 1-2 weeks post visit; and the RA who completes the SEGUE and completes the 4C coding, both off the audio.

The research records and data will be stored and destroyed in compliance with record Control Schedule (RCS) 10-1.

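### The arm-blinding claimed for SEGUE and 4C coders is not secured: two of the three listed coders also collect visit data, and recorder instructions differ between the arms compared

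*Combined protocol and SAP*

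**What the plan says.** Section 5.1 (Study Design) makes one blanket statement covering all three arms: "the members of the research team collecting the data and coding the audio are blinded as to study arm". Under Aim 2 it adds a safeguard for the ratings: "the audio coder will only have access to the designated codes for provider and patient", because codes are assigned and names stored separately as the first step after upload.

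Other parts of the protocol describe how the work is done:

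- Section 5.3: "the RA will meet patients (who have already assented by phone) prior to their appointment to complete the consent process".
- Section 5.2, item (C): the patient receives the recorder and "instructions based on the arm of the study to which they are randomized". It is kept in view in Arms 1 and 2 and hidden in Arm 3.
- Table 2 (Gantt chart): the row "SEGUE + 4C Coding of sample of recorded visits" lists three staff, two of whom are also on the audio data collection row. The PAM call row lists the same three staff as the data collection row.
- Section 7.0: those given need-based access to the crosswalk file include "the RA who completes the SEGUE and completes the 4C coding, both off the audio" and the RA who makes the PAM calls.
- Section 5.1, on recording technology: "Each audio file name will include the Veterans last name and date of the visit".
- Section 5.1 also says that SEGUE and 4C are completed with the medical record open.

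**The concern.** SEGUE and 4C are scored by staff listening to a recording, and hypotheses 2A and 2B state the expected direction: providers who know they are recorded score higher. A coder who knows whether the recorder was open or hidden can move the scores that way without intending to. Every Aim 2 outcome is of this kind, so protection against rater bias rests on the blinding statement. If the statement is not backed by a division of duties, the trial report could describe assessment as blinded without being able to show it.

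PAM is also collected by staff, in telephone interviews, and carries a smaller version of the same risk. Return visit adherence, refill coverage, blood pressure and A1c are extracted from the data warehouse and are not exposed to rater judgement.

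**Working it through.** **1. Aim 2, Arm 2 versus Arm 3.** Whoever gives the recorder instruction knows whether the visit is Arm 3. Sections 5.2 and 5.3 place an RA with the patient at that point. The COVID-19 modification keeps this meeting, shortened. Table 2 puts two of the three coders on the data collection row. No text available for this check bars a person from coding a visit that he or she handled.

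The code-only safeguard in section 5.1 would help if it held. Section 7.0 gives the coding RA the crosswalk, and coding is done in the patient's medical record, so the coder can know whose visit it is. Section 5.2 describes the crosswalk as linking a code to name and record number; nothing says it holds arm. The file name likewise shows surname and date. Identity therefore unblinds only a coder who already knows that patient's arm, which is the position of a coder who instructed the patient.

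In addition, section 5.5 item B labels the 4C record-extraction sample as Arm 3. Read literally, that batch would tell the extractor the arm.

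**2. Aim 1, PAM, Arm 1 versus Arm 2.** Both arms get the same open-recorder instruction, so the hand-out does not reveal this contrast. Section 5.1 says "Both patient and physician are blind to whether they are in Arm 1 or 2 until after the visit", but describes no mechanism for staff. Two later contacts could reveal Arm 1: the support voicemail that the site RA checks daily, since only Arm 1 patients have HealthPAL access to ask about, and the telephone call to patients who have not logged in within 7 days. The protocol does not name that caller, and the call falls around the start of the 1-2 week PAM window. Both contacts reach only some Arm 1 patients.

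**3. The plan's own figures.** Table 4.2 reproduces at a two-sided 5% level (assumed; the plan gives no alpha), ignoring clustering:

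- Probing, 32% versus 47%, 168 per arm: 80.6% (stated 80%).
- Planning, 59% versus 82%, 63 per arm: 81.6% (stated 82%).
- SEGUE, 17.5 versus 21, 250 per arm: above 99.9% (stated 99%).

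**4. Illustration for SEGUE.** Inputs from section 5.6: 250 per arm, SD 1.77 to 2.1.

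- SE = SD × √(2/250) = 0.158 (SD 1.77) or 0.188 (SD 2.1).
- Significance is reached at 1.96 × SE = 0.31 or 0.37 points, against a planned difference of 3.5.
- With no true effect and a rater-only difference b, the rejection probability is 1 − Φ(1.96 − b/SE) + Φ(−1.96 − b/SE). If only a share f of coded visits is affected, b becomes f × b.

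| Assumed shift | Share affected | Mean difference | SD 1.77 | SD 2.1 |
|---|---|---|---|---|
| 0.3 | all | 0.30 | 47% | 36% |
| 0.3 | one half | 0.15 | 16% | 13% |
| 0.3 | one third | 0.10 | 10% | 8% |
| 0.5 | all | 0.50 | 88% | 76% |
| 0.5 | one half | 0.25 | 35% | 27% |
| 0.5 | one third | 0.167 | 18% | 14% |

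**5. Illustration for 4C probing.** With 168 per arm and a 32% baseline, a 5-point coding differential on every visit has SE = √[(0.32×0.68 + 0.37×0.63)/168] = 0.052 and gives 16%. With a third to a half of visits affected (1.67 to 2.5 points) it gives 6 to 8%.

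The shift sizes and affected shares are assumptions; the protocol gives neither.

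**The case against.** The case on the other side has real force on four points.

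- A reader might infer that the access rules themselves disclose arm. They do not: the crosswalk and file names disclose identity, and section 5.1 says names are separated from recordings as the first step after upload.
- A reader might infer from the identical staff on the PAM and data collection rows that PAM callers know the arm. The documents do not support this. Arms 1 and 2 are instructed alike, the project manager uploads Arm 1 audio, and a script sends the link. Only the support contacts remain as a possible leak.
- Table 2 names responsible staff by phase, not by visit. Treating the data collection row as the people who hand out recorders is an inference from sections 5.2 and 5.3. One coder is not on that row, and the Cleveland RA, who is on it, is not a coder. The chart is compatible with nobody coding a visit they handled. Sections 1.0 and 4.0, on personnel, were not available for this check and may separate the duties.
- Rater discretion is limited: SEGUE is a checklist, and 4C uses pre-determined red flags with a stated inter-rater reliability of 90%. The largest error rates above require every coded visit to be affected.

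All four stand as limits on the point. None reconciles the code-only safeguard in section 5.1 with the crosswalk access in section 7.0, or supplies the missing rule on coding one's own visits. Agreement between raters does not exclude a bias that they share.

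**Conclusion.** The blanket blinding statement is not secured for SEGUE and 4C as the plan is written. The cause is overlapping duties combined with identifiable recordings. For PAM there is only a possible leak, through HealthPAL support and the day-7 call, to some Arm 1 patients.

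It would go too far to say that blinding failed or that the Aim 2 results will be biased: bias is possible and not shown. The size depends on assumptions. A 0.3-point SEGUE shift gives 36 to 47% false positives if every coded visit is affected, and 8 to 16% if a third to a half are (two-sided 5%, clustering ignored). A rater shift of that size could not account for the full planned 3.5-point difference, but it lies close to the 0.31 to 0.37 points that would be declared significant. The change is worth making before coding starts.

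**What to change.** 1. State that nobody codes an audio from a visit they enrolled or instructed. Assign such audios to the coder who is not on the data collection row, or to another coder who did not handle the visit. If one person handles each visit, at least two of the three listed coders remain eligible for every audio.
2. Reconcile sections 5.1 and 7.0 so that coders work from study codes, including the file name they see, with any record lookup not showing arm. Correct the Arm 3 label in section 5.5 if the extraction covers both arms.
3. Have HealthPAL support and day-7 calls for a patient handled by someone other than that patient's PAM caller.
4. Have coders log a guess of arm for each audio, and report the guesses against the true allocation.
5. Replace the blanket statement in section 5.1 with one saying who is blinded to which contrast.

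The cost is some scheduling effort and modest work to supply record data by study code, since 4C needs the record. The protocol does not show how many of the 500 audios the non-overlapping coder could take, so the cross-assignment in item 1 matters. No sample size changes. Talk on the recording may still reveal an open recorder; the arm guess measures this but does not remove it.
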